5.3.3. Discontinuation of Treatment

Patients who meet any of the discontinuation criteria will discontinue investigational treatment and will be followed up only for AEs until Day 14.

Study investigators may request the patient to discontinue investigational treatment in case of:

- Diagnosis of Grade 3 ankle sprain
- Any other medical condition requiring in the opinion of the investigator a change of the therapy for the baseline condition
- Occurrence of a medical condition requiring use of prohibited medications or treatment
- Medical condition affecting assessment of the primary endpoint
- Medical conditions affecting patient safety if the investigational therapy is continued: conditions and AEs causing safety concerns with investigational treatment to the ankle

joint area OR any other AE or condition that - in the opinion of the investigator – endangers patient safety if the investigational therapy is continued

- Lack of efficacy as considered by the investigator.

Discontinuation of investigational treatment and its reason will be documented in the medical records and recorded in the eCRF. If a patient discontinues investigational treatment, the discontinuation of treatment visit should be performed. Further treatment of the ankle sprain will be at discretion of the investigator and will not be recorded in the eCRF. In case the patient will be treated in another hospital or practice, the investigator will make efforts to collect and record AEs the patient might have had until Day 14. This can be done during an onsite visit or a phone call with the patient or with the treating physician at the other hospital or practice. Patients who discontinue prematurely from the study will not be replaced, except patients with Grade 3 sprain confirmed at any day up to Day 4 ('replacement' referring to the total number of patients to be enrolled, see also definitions in section 11.4).

5.3.4. Withdrawal of Patients from the Study

Reasons for premature withdrawal (drop out) from the study:

- Diagnosis of Grade 3 ankle sprain at any day up to Day 4
- The patient does not fulfil all inclusion criteria and/or meets any of the exclusion criteria but was randomised by error
- Pregnancy
- Lost to follow up
- Death
- Withdrawal of consent.

Withdrawal from study including its reason will be documented in the medical records and entered into the eCRF. In case the reason for withdrawal from study is withdrawal of consent, the patient will be asked why he/she withdrew his/her consent. The specified reason will be also recorded in the medical records and entered into the eCRF. No further investigational treatment will be used and/or assessments will be performed for withdrawn patients. In case of an ongoing AE, the patient is to be followed up according to the local medical practice.

5.3.5. Study Site Discontinuation by the Sponsor.

The Sponsor may prematurely close a study site at any time for any of the following reasons:

-
- occurrence of AEs or other safety issues requiring early withdrawal of at least 25% of enrolled patients (if 20 or more of planned patients are enrolled)
 - failure to enroll patients, i.e. no patients enrolled after 3 months from site initiation
 - persisting occurrence of significant protocol violations affecting patient safety in already enrolled patients
 - inaccurate or incomplete data affecting evaluability of patients in final analysis
 - significant administrative problems including GCP violations or misconduct of the study which may jeopardize the quality of study.

The reasons for the discontinuation of the study at a study site have to be communicated in writing to the IEC of the relevant site. Afterwards the close-out site visit has to be performed.

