5.1. Overall Design and Plan of the Study

This is a multicentre, double-blind, randomised, active- and placebo-controlled, parallel-group study.

After evaluation of entry criteria patients with grade 1 or 2 unilateral ankle sprain will be randomised to study treatment. The treatment will be 3 g of Traumed[®] gel or diclofenac gel or matching placebo gel, administered locally to sufficiently cover the area of the injury, 3 times daily for 7 days. The first treatment will be administered following the baseline study procedures and after randomisation of the patient on Day 1.

After end of investigational treatment patients will be followed up for another 7 days. Consequently, the entire duration of the study for each patient will be 14 days.

Patients will receive paracetamol (acetaminophen) 500 mg/tablet as rescue medication to be taken for pain relief when necessary (*pro re nata*, PRN) during the entire duration of the trial, see section 6.1.9 for further details. In addition, patients will not be allowed to take any pain relief medication other than the provided paracetamol, see section 6.2 for details.

All patients will receive soft support (elastic bandage) on Day 1. There will be a re-evaluation of grading of the disease at Day 4. Patients whose classification will be changed to Grade 3 will be withdrawn from the study. Grade 1 and grade 2 patients will continue using the soft support during the entire study, if required. Grade 2 patients will additionally receive a semi-rigid removable brace on Day 7, see section 6.1.10 for detailed description. It will be strongly recommended to all patients to use arm crutches during the entire trial and with a special importance until Day 4. The patients should only partly weight the sprained ankle when using crutches.

The study will start with the recruitment of the first patient. End of trial is defined as completion of the data base lock.

The study was originally planned to be started in Q1/2018. The first patient was screened on February 26th, 2018. The extended duration of the recruitment period will be approximately 35 months and will be completed when at least 808 eligible patients have been enrolled. (*revised per Amendment to protocol version 3.0*)

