9.2. Recording of Adverse Events

All AEs that occur during the entire course of the study after the patient has signed the informed consent are to be collected and reported in the eCRF, regardless of whether they are reported by the patient, elicited by investigator questioning, detected through physical examination, or by other means. These should include AEs observed at the site of administration of the IMP (lateral ankle) as well. AEs of Screening Failures will be documented on the paper *AE Reporting Form* as they will not be entered in the eCRF.

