11.1.1. Data Sets to be Analysed

Analyses will be based on the Safety Analysis, Full Analysis, and the Per-Protocol analysis sets. The definitions of the analysis sets follow those given in the ICH E9 guideline (CMP/ICH/363/96).

Safety Analysis Set: Randomised patients who receive at least one dose of investigational medication will form the Safety Analysis Set. The Safety Analysis Set will be used for all analyses of safety, tolerability, and background characteristics. For this set, the exposure to IMP will be also analysed.

Full Analysis Set (FAS): The Full Analysis Set is a subset of the Safety Analysis Set consisting of all patients with acute unilateral Grade 1 or Grade 2 sprain of the lateral

ankle, for whom both baseline and Day 4 VAS values of pain are available. The Full Analysis Set will be used for the Intent-to-Treat (ITT) analysis.

Per-Protocol (PP) Set: Patients in the Full Analysis Set without major protocol deviations will form the PP Set. The PP Set will be used for the per-protocol analysis of the efficacy parameters. The same efficacy evaluations as in the FAS are planned. Relevant differences between the FAS and PPS will be evaluated in the clinical trial report.

Protocol deviations will be collected during the entire study and will be classified as minor or major at the Blind Data Review Meeting (BDRM). Protocol deviations that may affect the efficacy outcome of participants will be classified as major. The decision about major protocol deviations and assignments to populations will be documented in the BDRM meeting minutes.

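### Dosed patients found ineligible after randomisation leave the study under Protocol 5.3.4, so new adverse events after withdrawal are not actively collected

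*Protocol*

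**What the plan says.** Protocol 5.3.4 gives as one reason for premature withdrawal from the study: "The patient does not fulfil all inclusion criteria and/or meets any of the exclusion criteria but was randomised by error". For everyone withdrawn it adds: "No further investigational treatment will be used and/or assessments will be performed for withdrawn patients". The one exception there reads: "In case of an ongoing AE, the patient is to be followed up according to the local medical practice".

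Three other sections bear on the same patients:

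- **Exposure.** Section 5.1: "The first treatment will be administered following the baseline study procedures and after randomisation of the patient on Day 1". Section 11.1.1: "Randomised patients who receive at least one dose of investigational medication will form the Safety Analysis Set". A patient randomised in error is therefore normally dosed and in the safety denominator.
- **Follow-up after stopping the gel.** Section 5.3.3: "Patients who meet any of the discontinuation criteria will discontinue investigational treatment and will be followed up only for AEs until Day 14". It allows this by visit or telephone, including contact with an outside physician. Ineligibility as such is not on the 5.3.3 list.
- **AE recording in general.** Section 9.2: "All AEs that occur during the entire course of the study after the patient has signed the informed consent are to be collected". Section 9.4 adds that AEs arising after a patient's own participation has ended are reported to the sponsor if the investigator sees an association with the product.

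On the efficacy side, the FAS (Protocol 11.1.1) is limited by sprain grade, laterality, and availability of baseline and Day 4 VAS. SAP 9.7.1.2 lets a carried-forward value count as the Day 4 value. SAP 9.5.1.2 imputes from the latest follow-up value. SAP 9.7.1.2 treats a baseline pain score below 50 as a major deviation, which removes the patient from the PP set and not from the FAS.

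**The concern.** Two decisions are tied together that need not be: whether a patient goes on using the gel, and whether the trial goes on observing that patient. Someone who stops the gel for lack of efficacy has a defined AE follow-up to Day 14. Someone who was dosed and then found to breach an entry criterion has none. Exclusion criterion 10 (sensitivity to a study-drug component, or reactions triggered by acetylsalicylic acid or NSAIDs) is among the criteria that can be missed, so this group may include patients whose later events are of particular interest.

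At stake is the completeness of the safety data. A patient who stays in the denominator but is no longer asked about AEs counts as event-free by default. The pain data raise a smaller, related issue: the analysis sets expect ineligible Grade 1 or 2 patients to stay in the FAS and be dealt with in the PP set, while 5.3.4 stops collecting the scores this needs.

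**Working it through.** **1. The AE rules side by side**

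| Situation | AEs ongoing at that time | New AEs judged associated | New AEs not judged associated |
|---|---|---|---|
| Stops treatment (5.3.3) | followed to Day 14 | collected to Day 14 | collected to Day 14 |
| Withdrawn as randomised in error (5.3.4, 9.4) | followed under local practice, no end day | reportable, not actively sought | no collection route |
| General rule (9.2) | collected | collected | collected |

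The gap is the last column of the second row, together with the absence of any scheduled contact. For a patient withdrawn on Day 1 it lasts up to 14 - 1 = 13 days. Grade 3 sprain stands on both the 5.3.3 and the 5.3.4 lists, with different follow-up, which shows that the two sections were not reconciled.

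**2. What happens to the primary endpoint**

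- Withdrawn before the Day 2 assessment: no follow-up value to carry forward, so not in the FAS.
- Withdrawn between Day 2 and Day 4: in the FAS, with the Day 2 score used for Day 4.
- Withdrawn after the Day 4 assessment: primary endpoint complete.

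**3. How many patients**

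The documents give no count. SAP section 8 gives major-violation rates of 1.9% (non-issue) and 11.4% (issue). A non-drug-related premature discontinuation, or a missing Visit 1 or Visit 3 score, is on the major list (SAP 9.7.1.2), so error-withdrawals should fall within these rates.

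- Non-issue: 808 - 184 = 624 planned; 0.019 x 624 = 11.9, about 12, across three arms and all causes.
- Issue cases, outside the confirmatory analyses: 0.114 x 184 = 21.0, about 21.

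The SAP does not state the denominators. If the non-issue rate was taken within the FAS, patients lost before Day 2 are not in it.

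**4. Size for the superiority test**

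The plan's own figure first: with difference 25, SD 75, two-sided 5%, 90% power and 2:1 allocation, placebo n = 1.5 x (1.960 + 1.282)^2 x (75/25)^2 = 142, and test gel 284. The plan uses 146 and 291 (power 90.8% by the normal formula).

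The Day 2 to Day 4 trapezoid is 2 days x (V2 + V4)/2 = V2 + V4. Carrying V2 forward makes it 2 x V2, so the patient's AUC rises by V2 - V4.

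- Assumed fall of 10, 20 or 30 mm: 10, 20 or 30 mm x days per patient.
- If 1.9% of an arm is affected: 0.019 x 10, 20, 30 = 0.19, 0.38, 0.57 mm x days on the arm mean. Equal shares in both arms cancel.
- Extreme case, all 12 in one arm with a 20 mm fall: placebo 12/156 x 20 = 1.5; test gel 12/312 x 20 = 0.8 mm x days.

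The planned difference is 25. If patients are lost instead of imputed, power at 312/156 goes from 92.5% (no loss) to 92.0% (2% loss).

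**5. Size for the AE-detection requirement**

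The plan's figure: ln(0.05)/ln(0.99) = 298.07, so 299; 299/0.96 = 311.5, so 312. With 312 test-gel patients the chance of seeing an AE of 1% incidence is 1 - 0.99^312 = 95.7%. If 2% contributed nothing (306 left) it is 1 - 0.99^306 = 95.4%. At 5% loss (296 left) it is 94.9%. These are upper limits on the loss, since withdrawn patients are observed until they leave.

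**The case against.** The strongest reply is that the gap is narrow and the numbers are small. Much of that stands.

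- **A reader might infer that AE follow-up is lost altogether.** It is not. Ongoing AEs are still followed, and 9.4 makes later AEs reportable if judged associated. A hypersensitivity reaction in a patient with a missed NSAID sensitivity is the kind of event 9.4 should catch. But that route relies on the patient coming forward and on a causality judgement. It does not replace the collection of all AEs that 9.2 calls for.
- **A reader might infer that contraindicated patients are bound to get less follow-up than those who stop the gel.** The documents do not settle this. The 5.3.3 list includes conditions that endanger the patient if treatment continues, which could cover some of them. The two sections overlap, and nothing says which prevails.
- **A reader might infer that the superiority analysis loses these patients' pain scores.** Scores before withdrawal are kept, LOCF retains anyone with a Day 2 score, and withdrawal after Day 4 costs the primary endpoint nothing. SAP 9.5.1.2 calls the number of missing efficacy values marginal. That section also drops the LPCF sensitivity analysis, so no alternative imputation tests the carried-forward scores. With so few values this matters little.
- **A broad remedy would go too far.** Deleting the entry from 5.3.4 would remove the only explicit stop of the gel for ineligibility as such. Placing every such patient in the FAS would contradict its grade and laterality condition. The pain assessment itself requires investigator-performed passive flexion, which may not suit every patient found ineligible.

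**Conclusion.** The point holds as a gap in safety data collection. For dosed patients withdrawn as randomised in error, new AEs after withdrawal are not actively sought, and those not judged associated have no route into the data. This conflicts with 9.2 and with the Day 14 follow-up in 5.3.3, while the patients remain in the Safety Analysis Set.

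The efficacy consequence is real but very small: about 0.4 mm x days on an arm mean and about 1.5 in a one-sided extreme, against 25, with a power loss of about half a percentage point. The documents do not support reading this as a threat to the superiority result or to the sample size.

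These sizes rest on three assumptions: that error-withdrawals lie within the SAP's 1.9% rate, that this rate applies to the planned 624 non-issue patients, and that pain falls by 10 to 30 mm between Day 2 and Day 4.

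**What to change.** Reconcile Protocol 5.3.3, 5.3.4, 9.2 and 9.4 so that leaving the study is separated from stopping the gel, without altering any rule on the gel:

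1. State that dosed patients found ineligible have all AEs collected to Day 14, by visit or telephone as 5.3.3 already allows, unless they withdraw consent.
2. State that VAS at the scheduled visits up to Day 4 is recorded where the investigator considers the assessment appropriate.
3. State that patients who meet the existing FAS definition (unilateral Grade 1 or 2) are analysed as randomised, with other eligibility failures handled in the PP set.
4. Settle which follow-up applies where a patient fits both 5.3.3 and 5.3.4, Grade 3 included.
5. Report by arm the number withdrawn as randomised in error, with the day of withdrawal.

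The cost is one protocol paragraph, one table row, and a few extra contacts for a small number of patients. The SAP postdates the database hard lock, so for data already collected only items 3 and 5 can still be acted on.

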5.3.6. Premature Termination or Temporary Suspension of the Study

Heel reserves the right to terminate this clinical study prematurely if, in the opinion of the investigator or Heel, an excessive risk exists or if continuation of the study does not appear to be reasonably justified (i.e. the study is not qualified to show efficacy or harmlessness of the IMP).

If the trial is prematurely terminated or suspended for any reason, the investigator must follow the instructions of the sponsor to stop the trial. The investigator should promptly inform all affected patients and should assure appropriate therapy and follow-up. Furthermore, the investigator should promptly inform the involved personnel of the institutions, where applicable.

In both cases, Heel will promptly inform the Competent Regulatory Authority and IEC and provide them with a detailed written explanation of the termination or suspension.

If the Competent Regulatory Authority or IEC terminates or suspends its approval or favorable opinion of a trial, the sponsor will inform the investigators and institutions and provide them with a detailed written explanation of the termination or suspension.

Suspended trials can only be restarted after re-approval or positive opinion from Competent Regulatory Authority and IEC.

If the investigator or institution terminates or suspends the trial at his/her site without prior agreement of the sponsor, the investigator or institution should promptly inform the sponsor and should provide the sponsor with a detailed written explanation of the termination or suspension. Depending on this communication the sponsor will inform IEC and Competent Regulatory Authority, in accordance with applicable regulations.

6. Study treatment

6.1.1. Description of Study Medication

Study medication will be provided by the Production Operations Department of Biologische Heilmittel Heel GmbH.

Investigational Medicinal Product (IMP)

| Ingredient | Traumed [®] gel, 100 g contains |
|--------------------------------------|--|
| Arnica montana D3 | 1.500 g |
| Calendula officinalis Ø ¹ | 0.450 g |
| Hamamelis virginiana Ø | 0.450 g |
| Echinacea Ø | 0.150 g |
| Echinacea purpurea Ø | 0.150 g |
| Matricaria recutita Ø | 0.150 g |
| Symphytum officinale D4 | 0.100 g |
| Bellis perennis Ø | 0.100 g |
| Hypericum perforatum D6 | 0.090 g |
| Achillea millefolium Ø | 0.090 g |
| Aconitum napellus D1 | 0.050 g |
| Atropa belladonna D1 | 0.050 g |
| Mercurius solubilis Hahnemanni D6 | 0.040 g |
| Hepar sulfuris D6 | 0.025 g |
| Excipients | contains purified water, ethanol, carbomers, sodium hydroxide solution |
| Ethanol content | 24,4 % (V/V) |
| Bulk Number | 9934 |

| Ingredient | placebo gel, 100 g contains |
|-----------------|--|
| Excipients | contains purified water, ethanol, carbomers, sodium hydroxide solution |
| Ethanol content | 24,4 % (V/V) |
| Bulk Number | 78980 |

The composition of the Diclofenac Heumann Gel (in the Study Protocol referred as 'diclofenac gel') is described in the "Fachinformation" as follows:

| Ingredient | Diclofenac Heumann Gel, (1%), 100 g contains |
|------------------------|--|
| Diclofenac sodium salt | 1,00 g |
| Excipients | contains purified water, ethanol, isopropanol, carbomers, ammonia solution |

¹ Ø Homeopathic mother tincture

6.1.2. Assigning Patients to Treatment Groups

Patients will be randomly allocated to Traumed[®] gel or diclofenac gel or placebo gel in 2:1:1 randomisation. A corresponding random code list is prepared using the random permuted block scheme. In accordance with the ICH Biostatistics Guideline, the block size is intentionally not given in the trial protocol [ICH E9 § 2.3.2, “Investigators and other relevant site staff should generally be blind to the block length”]. The sealed random code list and the sets of sealed envelopes are prepared using the validated program RANCODE in a validated working environment at idv Data Analysis and Study Planning, Gauting, Germany.

Patients will be randomised based on the 4-digit randomisation number recorded on the investigational medication (IMP). The next patient eligible for randomisation will be allocated to the lowest available randomisation number at the site. IMP will be provided to all sites in pre-defined shipment blocks and shipment blocks will contain appropriate distribution of randomisation codes belonging to the 3 treatment arms.

6.1.3. Dosage and Administration of IMP

Randomised patients will receive either Traumed[®] gel or diclofenac gel or placebo gel. The treatment regimen is 3 g of study drug applied by gentle rubbing to sufficiently cover the area of the injury 3 times daily for 7 days. Patients will use dosing card to administer an appropriate amount of the study drug.

The selection of dose and timing for each patient dosage and administration of IMP is in line with established clinical practice.

The team member responsible exclusively for handling the study medication will apply the first and last IMP dose during Screening/ Baseline Visit (Day 1) and End of Treatment (EoT) Visit 4 (Day 7), train all patients how to use the IMP with special regard to the dosage and how to use the dosing card and will ensure that they are trained for the application of the study medication.

6.1.4. Blinding

This is a double-blind, randomised study. Study personnel will be blinded during the study. The investigator will keep the sealed treatment (emergency) code envelopes throughout the course of the study and must not break the code without a valid reason (e.g. in case of emergency). Emergency unblinding is to be done only when absolutely necessary for the management of an individual patient and where stopping the blinded medication is not sufficient in the judgement of the investigator. The justification for the unblinding has to be discussed by telephone with the Sponsor’s responsible person to

ascertain whether unblinding is necessary and that appropriate steps for patient management are taken.

To further support the blinding each investigational site will have a team member responsible exclusively for handling the study medication and soft support/ semi-rigid brace, and who will not be involved in any other study procedures related to the patient (in the Study Protocol referred as team member responsible exclusively for handling the study medication). He/she will apply the first dose of investigational treatment and will train the patient how to use the dosing card and how to apply the study medication and the elastic bandage/ semi-rigid brace. The team member responsible exclusively for handling the study medication will remove the bandage at each visit before the investigator makes the investigations and will apply the IMP and replace the elastic bandage/ semi-rigid brace (as required as of Visit 4).

It will be ensured that only the team member responsible exclusively for handling the study medication will be present at the IMP gel applications and at removing and replacing the bandage/ semi-rigid brace. No other member of the investigator team will have any contact with the IMP for the entire duration of the study.

Disposable dosing cards will be used for each application. These cards will indicate the amount of IMP gel for each application and in addition due to the camouflage design they will also support the blinding of the patients.

The returned IMP will be stored in zipped bags closed by the team member responsible exclusively for handling the study medication until return to the sponsor for destruction.

Site staff of all investigational sites will receive a comprehensive training for these procedures at the investigator meeting as well as at the Site Initiation Visits. In addition, an agreement will be signed by all site personnel (principal investigator, investigator(s), study nurse(s) and team member(s) responsible exclusively for handling the study medication as a minimum) to ensure the procedures are understood and followed.

